#### **4.3 Subject and Trial Discontinuation**

Subjects may choose to withdraw from this study at any time for any reason without penalty of jeopardizing their health care or loss of benefits to which the subject is otherwise entitled.

Within the provisions of informed consent and good clinical judgment with respect to safety, every attempt will be made to have subjects complete the study. The following are reasons to terminate a subject's participation in the study:

1. Subject experiences an AE that in the judgement of the Investigator poses a significant risk to the subject for continued participation in the study.
  - a. If a subject experiences hyperglycemia, defined in Section 7.3.2, blood glucose will be checked 1-2 hours later. If the glucose remains elevated, the subject will be withdrawn from the study.
2. Subject uses a prohibited medication (listed in Section 5.7) that in the judgment of the Investigator poses a significant risk to the subject for continued participation in the study or that will interfere with the interpretation of the results of the study.
3. Subject becomes pregnant.
4. Significant protocol violation or noncompliance on the part of the subject or the Investigator.
5. Intercurrent illness that requires treatment that is not consistent with the protocol requirements, or intercurrent illness or the associated treatment that in the judgment of the Investigator poses a significant risk to the subject for continued participation in the study.
6. Subject wishes to withdraw for any reason.
7. Sponsor elects to end the study, or the Investigational Site elects to end the study at their site.
8. Any other reason that in the judgment of the Investigator poses unacceptable risk to the subject.

Reasons for study drug discontinuation may include the following:

1. Adverse event
2. Episodes of hypoglycemia as defined in Section 7.3.1.
3. Subject meets one of the exclusion criteria during the study
4. Any clinically significant change in the subject's medical condition

Subjects who withdraw from the study prior to treatment may be replaced. Subjects who are withdrawn and have received at least one treatment will not be replaced. Subjects who discontinue study drug treatment will not be replaced.

Except in cases of emergency, the Investigator should consult with the Sponsor and the Medical Monitor before removing the subject from the study. In some circumstances it may be necessary to temporarily interrupt treatment as a result of AEs that may have an unclear relationship to study treatment. The Investigator should obtain approval from the Sponsor and Medical Monitor before restarting study treatments that were temporarily discontinued for an AE.

In the event that a subject discontinues the study prior to completion, the date the subject is withdrawn and the reason for discontinuation will be recorded in the source documents and CRF. Although a subject will not be obliged to give his/her reason for withdrawing prematurely, the Investigator will make a reasonable effort to obtain the reason while fully respecting the subject's rights.

All subjects who are randomized and treated (i.e., received any amount of study treatment) will be included in the safety analyses. Thus, every effort will be made to contact any subject who fails to attend any appointments/contacts, in order to ensure that he/she is in satisfactory health. If a subject withdraws from the study as a result of meeting discontinuation criteria after the start of study treatment administration, reasonable efforts should be made to have the subject return for the early withdrawal evaluations (Section 3.9). Any subject withdrawn due to a suspected study treatment -related AE should be followed until resolution or stabilization of the event.

Subjects may choose to withdraw authorization to use and disclose their PHI as defined by the HIPAA. Such withdrawal of authorization must be made to the Investigator in writing. Any PHI collected by the Investigator prior to the date of such withdrawal will continue to be used and disclosed.

Randomized subjects who are discontinued from this study for any reason will not be replaced.

The Sponsor has the right to terminate this study, and the Investigator/Investigational Site has the right to close the site, at any time, although this should occur only after consultation between involved parties. The Investigator will notify the IRB in writing of a premature termination of a study or closure of Investigational Site and will send a copy of the notification to the Sponsor.

Events that may trigger premature termination of a study or closure of an Investigational Site include, but are not limited to, a new toxicity finding, a request to discontinue the trial from a regulatory authority, non-compliance with the protocol, GCP violations, slow recruitment/low enrollment, or change in development plans for the study treatment.

If either of the criteria listed below is met, enrollment of new subjects and dosing of ongoing subjects will be temporarily stopped. The Investigator, Sponsor, and the Medical Monitor will discuss whether a lower dose or any additional treatment guidelines should be implemented, or if the trial should be permanently stopped. Any proposed changes to the protocol to address such findings will be submitted for review and approval by the IRB and FDA prior to re-starting the trial.

1. A death within 30 days after study treatment administration where there is a reasonable possibility that the drug caused the event;
2. Two Grade 4 AEs where there is a reasonable possibility that the study treatment caused the events.

## 5 STUDY TREATMENT

### 5.1 Description of Investigational Drug

**Name of the IMP:** ORMD-0801

**Dose and dosage regimen:**

1. Treatment A: 24 mg (16 mg + 8 mg capsules) Once Daily (QD) at Bedtime
2. Treatment B: 8 mg (8 mg capsule) three times a day (TID) 45-90 minutes before meals
3. Placebo: Placebo capsules QD at bedtime during placebo run-in period 10 days prior to randomization.

**Formulation:** Coated soft gel capsule [SBTI], disodium EDTA, fish oil, aerosol, and Tween 80

**Mode of administration:** Oral

#### 5.1.1 Packaging and Labeling

This study is an open label study. All study medication including Placebo will be shipped to site. The Investigational Site pharmacist will be responsible for dispensing the appropriate treatment based on the randomization schedule. Study medication will be dispensed to the site with instructions for treatment administration.

The treatment packages will be labeled with the following information:

- Study number
- Subject ID
- Kit No./Bottle ID
- Dosage Form/Content
- Directions for use, including route of administration
- Number of capsules in package
- Storage conditions
- Instructions to “keep out of reach of children”
- Caution: New Drug – Limited by Federal (or United States) law to investigational use.
- Name of Sponsor

#### 5.1.2 Storage and Handling

All study treatment must be kept in an appropriate, secure area to prevent unauthorized access. The study treatment is to be shipped under refrigerated conditions and stored in the original packaging at controlled temperature (36 to 46°F; 2 to 8°C). Excessive humidity should be avoided. Storage conditions will be monitored and appropriate monitoring logs maintained as source data. Deviations from the established temperature, as well as the occurrence of excessive humidity, should be documented, and the Sponsor should be notified.

## **5.2 Randomization**

This is a randomized, open label, crossover study. Approximately 26 eligible subjects with T1D will be randomized to all 2 treatment schedules.

Integrium, LLC will generate and implement the randomization procedures for this trial. A computer-generated randomization schedule will be used for assigning treatment schedules. The Investigational Site pharmacist will follow this randomization schedule to dispense the appropriate study treatment.

## **5.3 Study Treatment Administration**

All subjects will receive Placebo capsules once a day at bedtime during placebo run-in period for 10 days prior to randomization.

Subjects receiving Treatment A should take 16 mg + 8 mg capsules once a day at bedtime.

Subjects receiving Treatment B should take 8 mg capsule three times a day 45-90 minutes before meals.

## **5.4 Dose Modifications**

This study does not include any planned dose modifications. Subjects will consume study treatment orally at the assigned (randomized) dose unless discontinuation criteria as defined in Section 4.3 are met.

## **5.5 Measuring Subject Compliance**

Treatment compliance will be ascertained by accountability of returned IMP and recording in diary.

## **5.6 Drug Accountability**

In accordance with current GCP, the Investigational Site will account for all study treatment supplies. Details of receipt, storage, administration, and return or destruction will be recorded in the Investigational Drug accountability record according to the SOP of the Investigational Site. Copies of the Investigational Drug accountability record will be provided to the Sponsor.

Study treatment will only be dispensed to subjects enrolled in this protocol, and only as directed by this protocol. Administration of study treatment will be accurately recorded in each subject's source documents and eCRF.

## 5.7 Concomitant Medications and Supplements

All medications and supplements (other than study treatment) taken by the subject from Visit 3/Day 1 through Visit 7 will be considered “concomitant” medications and supplements.

Medications and supplements taken prior to Visit 3/Day 1 that are no longer being taken at the time of Visit 3/Day 1 will be considered “prior” medications and supplements.

All prior medications and supplements taken within 30 days prior to the first dose of study treatment and concomitant medications and supplements will be recorded in the subject’s source documentation and in the eCRF.

The use of concomitant medications and supplements should be kept at a minimum, if possible. Any medications and supplements needed for the welfare of a subject and that in the judgment of the Investigator will not pose a significant risk to the subject for continued participation in the study or that will not interfere with the interpretation of the results of this study may be given to the subject. If a subject requires the use of any of the prohibited medications and supplements listed below, the Investigator will contact the Sponsor and the Medical Monitor to discuss the subject’s continued participation in the study. In the event of an emergency, subjects will be treated at the discretion of the Investigator according to acceptable community standards of medical care.

The following are prohibited medications:

1. Any Investigational Drug other than ORMD-0801 within 30 days prior to Visit 3/Day 1 through Visit 7;
2. Any anti-diabetic drugs (except for those allowable by the inclusion criteria) including GLP-1 analogue,  $\alpha$ -glucosidase inhibitors, glinides, and pramlintide within 6 weeks prior to Screening;
3. Thyroid preparations or thyroxine (except in subjects on stable replacement therapy);
4. Systemic long-acting corticosteroids or other systemic corticosteroids or inhaled corticosteroids (if daily dosage is  $> 1,000 \mu\text{g}$  equivalent beclomethasone). Intra-articular and/or topical corticosteroids are not considered systemic.
5. Medications known to modify glucose metabolism or to decrease the ability to recover from hypoglycemia such as oral, parenteral, and inhaled steroids, and immunosuppressive or immunomodulating agents.

If the subject initiates prohibited drug therapy, or if the Investigator determines that use of a prohibited therapy is in the best interest of the subject’s health and well-being, the Investigator and sponsor will jointly decide to continue or discontinue the subject.

## 5.8 Dietary Restrictions

Subjects will be advised not to make any drastic changes in their regular diet throughout the study. Excessive caffeine use (i.e., more than five cups of caffeinated beverages per day) should

be avoided from Screening through Visit 7. Excessive alcohol use or binge drinking will be discouraged during the study.

Subjects will also be asked to refrain from any unusual or unaccustomed vigorous exercise during the course of the study.

## 6 STUDY PROCEDURES AND ASSESSMENTS

### 6.1 Informed Consent

According to the ICH guideline for GCP (E6) and all institutional local, state, and federal laws, the Investigator will obtain and document informed consent for each subject screened for this study. All subjects will be informed in writing of the nature of the protocol and Investigational Drug, its possible hazards, and their right to withdraw at any time, and will sign a form (ICF) indicating their consent to participate in the study prior to the initiation of study procedures. The subject's medical record should contain written documentation indicating that informed consent was obtained. The ICF must be reviewed and approved by the Investigator's designated IRB and by Oramed Ltd. designee prior to its use. Refer to Section 11.2.4 for further details regarding informed consent.

### 6.2 Medical History and Prior Medications

At Screening, a complete medical history (including start date of T1DM) will be collected by subject interview. Medications and supplements, recent blood donations, illnesses, and participation in other Investigational Drug trials or clinical trials will also be recorded.

### 6.3 Safety Assessments

#### 6.3.1 Weight and Height

Weight will be measured at visits as described in Table 1. Height will be measured at Screening only with the subject wearing no shoes.

#### 6.3.2 Vital Signs

Vital signs (including seated SBP/DBP, and heart rate) will be recorded at visits as described in Table 1. Blood pressure and heart rate will be measured after the subject has been sitting for at least 5 minutes in a quiet environment and prior to any blood draw that occurs at the same time point. The recorded seated SBP/DBP value will be the mean of two measurements taken 2 minutes apart and always using the non-dominant arm.

#### 6.3.3 Physical Examination

A physical examination will be performed at visits as described in Table 1, or in case of Early Withdrawal. The physical examination will include the following organ or body system assessments: skin; head, eyes, ears, nose, and throat; thyroid; lungs; cardiovascular; abdomen (liver, spleen); lymph nodes; and extremities, as well as an abbreviated neurological examination.

#### 6.3.4 12-Lead ECG

A 12-lead ECG will be performed at Screening. The 12-lead ECG will be recorded after the subject has been resting at least 5 minutes in the supine position in a quiet environment. ECGs

will be read for QT and QTc (Federicia's) intervals and clinically significant abnormalities. At the Investigator's discretion, an additional ECG may be performed at the end of treatment; however, it will be recorded in source documents as an unscheduled assessment.

### 6.3.5 Clinical Laboratory Tests

Blood and urine for clinical safety laboratory assessments will be collected and processed using standard procedures. A central laboratory will perform all clinical laboratory tests.

In the event of abnormal clinical laboratory values, the Investigator will make a judgment whether or not the abnormality is clinically significant.

#### 6.3.5.1 Clinical Safety Labs

The clinical safety labs will include the following hematology, serum chemistry, and urinalysis tests:

##### Hematology

- Hematocrit
- Hemoglobin
- Mean corpuscular hemoglobin
- Mean corpuscular hemoglobin concentration
- Mean corpuscular volume
- Platelet count
- Red blood cell distribution width
- Red blood cell count
- White blood cell count with differential

##### Serum Chemistry

- Sodium
- Potassium
- Chloride
- Bicarbonate
- Alanine aminotransferase (ALT)
- Aspartate aminotransferase (AST)
- Gamma-glutamyltransferase (GGT)
- Total bilirubin
- Alkaline phosphatase
- Albumin
- Total Protein
- Blood urea nitrogen (BUN)
- Creatinine
- Uric acid

- Glucose
- Calcium
- Phosphorus
- Total cholesterol
- Triglycerides

#### Urinalysis

- Appearance (color and character)
- Bilirubin
- Urobilinogen
- Protein
- Glucose
- Ketones
- Leukocyte esterase
- Urine blood
- Nitrite
- pH
- Specific gravity

#### Pregnancy Test

##### 6.3.5.2 Follicle Stimulating Hormone Test

A serum FSH test will be performed in postmenopausal women.

##### 6.3.5.3 Additional Screening Bloodwork

In addition to the blood tests listed above, infectious serology (HIV, HCV, and HBV), FPG, HbA1c, C-peptide, and TSH will be measured at Screening. FPG and HbA1c will be performed at visits as described in Table 1 and in case of Early Withdrawal.

#### 6.3.6 Continuous Glucose Monitor (CGM)

CGM will be used to monitor subject glucose levels (including post-prandial) throughout the study. Further information about the device can be found in the laboratory manual.

Subjects will have the CGM implanted at visits as described in Table 1. The device will be removed and the data will be downloaded at each subsequent visit. Staff will be advised regarding appropriate procedures in the event of nocturnal hypoglycemia.

## **6.4 Review and Documentation of Medications and Supplements**

All medications or supplements subjects are taking or have taken within 30 days prior to Visit 3/Day 1 through Visit 7 will be recorded in the subject's medical record and the medical history CRF.

All medications and supplements (other than study treatment) taken by the subject after Visit 3/Day 1 through Visit 7 assessments will be considered "concomitant" medications and supplements. Medications and supplements taken prior to Visit 3/Day 1 that are no longer being taken at Visit 3/Day 1 will be considered "prior" medications and supplements.

Medications and supplements should be recorded according to the generic name when possible. The use of concomitant medications and supplements should be limited to those that are medically necessary. Any medication or supplement used should have an indication recorded, and for concomitant medications and supplements, this indication must be represented as either for the treatment of an AE, for the management of a pre-existing condition, or for prophylaxis.

Dosage increases for any concomitant medication or supplement should be noted and the reason for the dosage increase recorded as an AE (assumes worsening condition). The side effects of concomitant medications will be recorded as AEs.

Any subject whose condition becomes disqualifying during the course of the study may be treated for that condition. If the condition is suspected during Screening, the subject should not be enrolled. Treatment of the condition should be instituted according to the Investigator's/attending physician's judgment.

Medications that have no treatment intent but rather are part of supportive routine care such as local anesthetics, intravenous solutions to maintain fluid balance and keep access open, medications used for prophylaxis, and narcotics for postsurgical pain must also be recorded in the subject's medical record and CRF.

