## 3 INVESTIGATIONAL PLAN

### 3.1 Overall Study Design and Plan

This study is designed to compare ORMD-0801 given QD versus TID in subjects with T1D. The study will consist of seven visits (including Screening Visit).

During Screening, subjects will be required to sign the informed consent form. Medical and medication history and demographic information will be collected. Eligibility for participation will be evaluated. Vital signs (height, weight, seated SBP/DBP, and heart rate) will be measured, physical examination will be performed, and a blood and urine sample will be collected for hematology/chemistry/urinalysis.

Eligible subjects will be scheduled to return to the clinic in 1 week (Visit 2). Subjects fulfilling all inclusion/exclusion criteria will have a CGM placed, provided with a diary, dispensed placebo capsules and asked to return to the clinic in 10 days (Visit 3, Day 1) for randomization. At Visit 3, data from CGM will be downloaded and diaries will be collected. Blood samples

will be collected in fasting for chemistry and HbA1C. Subjects will be randomized to receive either ORMD-0801 24 mg given once daily at bedtime, or ORMD-0801 8 mg given three times a day, 45-90 minutes before meals. Subjects will be instructed to continue their normal diet, and to adjust their basal and bolus insulin in the normal fashion. Subjects will be instructed to return to the clinic in 10 days before Visit 5 (Visit 4, Day 18). At Visit 4, compliance will be assessed, IMP and diary dispensed and the CGM will be placed. Subjects will be instructed to return to the clinic in 10 days for Visit 5 (Day 28). At Visit 5 a blood sample for chemistry panel and HbA1C will be drawn, the diary collected, the CGM removed and the patient will be crossed over to the alternate treatment regimen. IMP will be dispensed, and the subject will be asked to return in 10 days before Visit 7 for Visit 6 (Day 46). At Visit 6, compliance will be checked, IMP and a diary will be dispensed and the CGM will be placed. Subjects will be instructed to return in 10 days for Visit 7 (Day 56). At Visit 7 the CGM will be removed, the diary will be collected, compliance checked, blood sample will be drawn for a chemistry panel and HbA1C. A physical examination will be performed, and the subject will exit the study.

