## 4 STUDY SUBJECT SELECTION

### 4.1 Inclusion Criteria

Each subject must meet all of the following criteria to be eligible for study participation:

1. Male and female (non-childbearing potential) subjects aged 18 and older.
2. Body mass index (BMI) of 19-30 kg/m^2 at Screening and stable weight, with no more than 5 kg gain or loss in the 3 months prior to Screening.
3. T1D subjects must have:
  - a. A documented history of type 1 diabetes for at least 6 months
  - b. Should be on an MDI regimen
  - c. C peptide levels of < 0.7 ng/mL
  - d. HbA1C  $\geq$  6.5% to  $\leq$  10%
4. Females of childbearing potential must have a negative serum pregnancy test result at Screening.
5. Females who are not of childbearing potential are defined as:
  - a. post-menopausal (defined as at least 12 months with no menses in women  $\geq$  45 years of age) or
  - b. has had a hysterectomy and/or bilateral oophorectomy, or had bilateral tubal ligation or occlusion at least 6 weeks prior to Screening
6. Subjects who are of childbearing potential must:
  - a. agree to remain abstinent from heterosexual activity† or agree to use (or have their partner use) acceptable contraception to prevent pregnancy within the projected duration of the trial and for 14 days after the last dose of blinded investigational product. Two methods of contraception will be used to avoid pregnancy. Acceptable combinations of methods include:
    - i. Use of one of the following double-barrier methods: diaphragm with spermicide and a condom; cervical cap and a condom; or a contraceptive sponge and condom
    - ii. Use of hormonal contraception (any registered and marketed contraceptive agent that contains an estrogen and/or a progestational agent [including oral, subcutaneous, intrauterine and intramuscular agents, and cutaneous patch]) with one of the following: diaphragm with spermicide; cervical cap; contraceptive sponge; condom; vasectomy; or IUD.
    - iii. Use of an IUD with one of the following: condom; diaphragm with spermicide; contraceptive sponge; vasectomy; or hormonal contraception (see above).
    - iv. Vasectomy with one of the following: diaphragm with spermicide; cervical cap; contraceptive sponge; condom; IUD; or hormonal contraception (see above).

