2.6. Prior and Concomitant Medications

Prior and concomitant medications will be coded using World Health Organization (WHO) Drug dictionary March 2018 version.

Prior medications will be defined as any medication that stops prior to the day of first dose.

Concomitant medications will be defined as any medication that stops on or after the day of first dose.

Section 2.13 describes the imputation rules for partial dates. All medications will be presented in a data listing.

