2.7. Safety Evaluations

2.7.1. Adverse Events

Adverse events will be coded using the Medical Dictionary for Drug Regulatory Affairs (MedDRA) version 21.0 and tabulated, including categorical information of interest such as onset and resolution times, time of onset relative to dose, severity at onset, maximum severity, causal relationship to study medication, and action taken.

Treatment-emergent adverse events (TEAEs) are defined as any AE that starts or increases in severity after the first randomized dose of study treatment. The incidence of TEAEs will be tabulated by MedDRA preferred term, system organ class, treatment group, severity, and assigned relationship to study treatment. Adverse events will also be summarized by severity and relationship to the investigational product (IP).

The incidence of serious AEs, drug-related AEs, serious and drug-related AEs, and any AEs resulting in discontinuation from the study will be listed.

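### Section 6.4's rule on dose increases does not exempt the subjects' own insulin, so read literally it records protocol-permitted insulin increases, but not decreases, as adverse events

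*Protocol*

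**What the plan says.** Protocol Section 6.4 states: "Dosage increases for any concomitant medication or supplement should be noted and the reason for the dosage increase recorded as an AE". A parenthesis closing that sentence presumes that the condition has worsened.

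The definition of concomitant medication is broad in all three places that matter here:

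- Protocol 5.7: "All medications and supplements (other than study treatment) taken by the subject from Visit 3/Day 1 through Visit 7 will be considered" concomitant.
- Protocol 6.4 has the same scope: "All medications and supplements (other than study treatment) taken by the subject after Visit 3/Day 1 through Visit 7 assessments will be considered" concomitant.
- SAP 2.6: "Concomitant medications will be defined as any medication that stops on or after the day of first dose".

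The two protocol definitions carve out only study treatment, and the SAP definition carves out nothing.

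On background insulin, inclusion criterion 3b in Protocol 4.1 reads "Should be on an MDI regimen", and Protocol 3.1 instructs subjects "to adjust their basal and bolus insulin in the normal fashion". The amount of basal, bolus and total insulin over the final 10 days of each period is primary endpoint 1 (Protocol 2.2, SAP 2.8).

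On reporting, an adverse event that starts or worsens after the first randomized dose is a TEAE (Protocol 7.2, SAP 2.7.1). SAP 2.7.1 adds: "The incidence of TEAEs will be tabulated by MedDRA preferred term, system organ class, treatment group, severity, and assigned relationship to study treatment". Protocol 8.6.2 gives incidence as the number and percentage of subjects, and shows greatest severity and worst-case attribution when a subject has the same TEAE more than once.

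**The concern.** Injected insulin is both an efficacy measurement and, by definition, a concomitant medication. Subjects are expected to change it, in both directions, throughout the study. A rule that records the reason for any concomitant dose increase as an adverse event, and presumes worsening, therefore reaches into ordinary self-management.

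Safety is assessed mainly through adverse events (Protocol 8.1), in an open-label comparison at 3 sites. Three things are at stake:

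- The overall TEAE row, and the severity and relationship summaries, could be raised by entries that reflect titration rather than harm.
- The contamination runs one way, because an increase can create an adverse event and a decrease cannot.
- Section 6.4 and Section 7.2 point in different directions for the same insulin change. One site could log many such events and another none.

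**Working it through.** The documents state no figure on this point, so there is nothing to reproduce. The check has two parts.

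**1. Tracing the text**

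| Step | Source | What follows |
|---|---|---|
| Scope of concomitant medication | Protocol 5.7, 6.4; SAP 2.6 | Subject's own insulin is included |
| Entry requirement | Protocol 4.1, criterion 3b | Subjects take such insulin |
| Instruction | Protocol 3.1 | Increases and decreases are expected |
| Recording rule | Protocol 6.4 | Reason for an increase is recorded as an adverse event; no matching rule for a decrease |
| Timing | Protocol 7.2, SAP 2.7.1 | After the first randomized dose it is a TEAE |
| Reporting | Protocol 8.6.2, SAP 2.7.1 | It enters the tables by treatment group |

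A search for an exemption found none. Protocol 7.2, 7.3.1, 7.3.2, 7.4 and 8.6.2 and SAP 2.7.1 and 2.7.2 do not mention one. The nearest carve-out, in the list of prohibited drugs in Protocol 5.7, allows the anti-diabetic drugs that the inclusion criteria permit. It concerns what may be taken, not what is recorded as an adverse event.

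Section 7.2 defines an adverse event as an untoward medical occurrence, and Section 7.3.2 sets hyperglycemia at a reading above 300 mg/dL. Section 6.4 has no such threshold: it applies to an increase at any glucose level and for any reason.

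**2. Illustration of size**

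Let p be the probability that a subject increases insulin on a given day. The documents do not give p, so the values below are assumptions, and days are treated as independent. The chance of at least one increase in d days is 1 − (1 − p)^d. The subject counts use 26, the number planned in SAP 2.11 (Protocol 8.1 says 24). The percentages do not depend on it.

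| Assumed p | 28-day period | Subjects of 26 | 10 diary days | Subjects of 26 |
|---|---|---|---|---|
| 0.01 | 1 − 0.99^28 = 24.5% | 6.4 | 9.6% | 2.5 |
| 0.05 | 1 − 0.95^28 = 76.2% | 19.8 | 40.1% | 10.4 |
| 0.10 | 1 − 0.90^28 = 94.8% | 24.6 | 65.1% | 16.9 |
| 0.20 | 1 − 0.80^28 = 99.8% | 25.9 | 89.3% | 23.2 |

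The 10-day columns matter because the diary captures daily insulin only in the CGM windows (Protocol 3.1). Outside them, no passage provides for daily insulin capture, so fewer increases may come to a site's notice. The figures are the share of subjects for whom the rule could be triggered. They do not predict how many entries the sites would make.

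**The case against.** **The rule concerns the reason, not the increase.** Read together with Sections 7.2 and 7.4, Section 6.4 could be confined to real worsening. A larger meal is not an untoward occurrence, and a meal-to-meal bolus within normal practice may not be a dosage increase at all. This reading is available, so it cannot be said that every insulin increase becomes an adverse event. But the text says any concomitant medication and presumes worsening, so the literal reading is available too. That two readings are possible is itself part of the problem.

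**The tables limit the damage.** Incidence counts subjects, so many entries of one kind in one subject become one line. Entries under their own preferred terms leave the counts for other terms unchanged, and SAP 2.7.2 takes hypoglycemia from a separate log. This stands. A reader might infer that real adverse reactions would be buried; the table structure does not support that.

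**Bias between regimens is not shown.** A reader might infer that the regimen needing more injected insulin must show more TEAEs. That does not follow. The rule responds to increases, whereas the endpoint is the amount used in the final 10 days: a high but steady dose triggers nothing. If increases are common, both regimens approach the ceiling (94.8% against 99.8% for assumed p of 0.10 and 0.20), which leaves little room for a difference. Every subject is also planned to receive both regimens, so a site's reading of the rule should apply to both. What remains is that the rule counts in one direction, which could favour one regimen if the frequency of increases differs between them.

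**Decreases are not lost.** The diary records daily insulin in both directions during the 10-day windows, and SAP Listing 16.2.6.1 shows it. Only the adverse-event rule is one-sided.

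**Conclusion.** The concern holds as a conflict in the text. Section 6.4, with the definitions in Section 5.7, brings protocol-permitted insulin increases within an adverse-event rule. Section 3.1 invites those increases, and Section 7.2 would not by itself call them adverse events. No passage settles which governs.

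The consequence is possible inflation of the any-TEAE, severity and relationship summaries, and recording that may differ between sites. The analysis of the primary endpoints is not affected, and neither are the counts for unrelated preferred terms. The amount of inflation cannot be known from the documents. The range of 24.5% to 99.8% of subjects per 28-day period rests entirely on the assumed daily probabilities of 0.01 to 0.20, on independence between days, and on sites applying the rule literally and learning of every increase.

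The change is worth making because it costs little and the safety evaluation leans mainly on adverse events.

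**What to change.** Reconcile Section 6.4 with Sections 3.1 and 7.2 by adding, for example:

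*Routine adjustment of the subject's basal and bolus insulin is not in itself an AE under this rule; an AE is recorded only when the reason for the change is an untoward medical occurrence under 7.2 or 7.4, and hypoglycemia and hyperglycemia are reported under 7.3.1 and 7.3.2.*

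The reference to Sections 7.2 and 7.4 is deliberate. A blanket exemption for all insulin changes could lose genuine worsening that stays below the 300 mg/dL threshold in Section 7.3.2.

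If entries have already been made solely because of insulin titration, identify them before database lock and tabulate them apart from other TEAEs in Tables 14.3.1.1 to 14.3.1.6, with a line in SAP 2.7.1 to say so.

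The cost is one sentence in the protocol, with the IRB approval that Section 10 requires for an amendment, a matching instruction to the 3 sites, and one line in the SAP. No new data or subjects are needed, and no treatment instruction changes.
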